This statistical analysis plan covers the interim and final analyses of the Oncopain study T2001-01. As specified in the study protocol, the interim analysis will be executed as soon as 60 patients have completed the study.

The primary objective of the complete study consists in finding predictive factors of pain management and analgesic treatment efficacy in patients suffering from CIBP (cancer-induced bone pain). The analyses necessary to achieve this objective are very complex to conduct, due to the complexity of the data available. Secondary objectives describe intermediate milestones which will be reached during these analyses.

An interim analysis is also planned for the validation of sample size and necessary items among the personality tests.

All statistical analyses related to the study will be the responsibility of DNAlytics or designee. They will be conducted on the full analysis set. This set includes all data from patients who have been screened and who completed the study (no drop-outs). No safety analyses will be conducted during the interim study. The safety analyses on the complete database will be performed by the sponsor and reported in the Clinical Study Report. Additional exploratory analyses of the data will be conducted as deemed appropriate.

All hypothesis tests will be conducted at a two-sided alpha level of 0.05, unless otherwise stated.

Name	Company	Role
[name]	DNAlytics	Study design, analysis implementation, reporting
[name]	DNAlytics	Study design, analysis review, reporting
[name]	DNAlytics	Study design, analysis and report review
[name]	Tools4Patient	Study design. As study sponsor representative, monitors data analysis progress.

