2.3 Interim Objectives

- 1. To confirm the considered sample size of approximately 140 patients completing this study
- 2. To confirm questionnaires and historical data to be collected

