5.1.3 A1.3: Outlier detection and clustering

Population outliers will be detected through a principal component analysis (PCA) visualization, reported in Figure (1). The percentage of variance captured will be documented. The patients will be colored by their study center in order to detect possible differences among the centers.

Outliers might be removed for at least parts of the further analyses. Such cases will be documented.

A clustering procedure, namely an ensemble k-Means, will be applied in order to identify subgroups of patients with intra-group similar variables at baseline, and inter-group different variables at baseline. Table (tab-v1-clustering-desc) will report per-cluster univariate statistics (median, first and third quartiles) for all variables used in the clustering procedure.

A1.4: Correlation analysis 5.1.4

The correlation between each variable (personality traits and sociodemographic variables) and the pain at baseline (APS, WPS, BPI severity, interference and QLQ-C30) will be assessed. Statistical tests for non-zero Spearman's correlation will be used. For categorial variables, exact Fisher tests will be used. Correction for multiple testing will be applied. Results will be reported in Table (tab-v1-correlations) and Figure (2). Scatterplots of the significant correlations will be produced. Figure (3) will detail the correlations within pain assessment variables and Figure (4) the correlations between personality traits and pain assessment.

5.2A2: Evolution of daily pain and treatments

Pain evolution will first be analysed on its own (secondary objective 3, i.e. without linking it to the evolution of treatments). Then, the evolution of analgesic therapies are studied, as well as their correlation with pain evolution. Due to the complexity of treatments combinations for each patient and their frequent adaptation during the follow-up period, this analysis will be made on a simple summary of the therapy evolution. Finally, the interest of each variable characterizing the patient at baseline is evaluated for its relation with the pain evolution profile.

A2.1: Summary of individual pain evolution 5.2.1

Feature extraction will be performed in order to summarize each per-patient APS evolution curve into 3 meaningful variables:

- mean APS value
- linear trend of APS
- variability of APS around trend

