5.2.3 A2.3: Relation between patient's characteristics and pain evolution

For each feature from the patient characteristics at V1, the correlation will be computed with the linear trend of pain evolution defined in A2.1. A p-value for non-zero correlation will be reported too, with BH correction for multiple testing. Results will be presented in Table (tab-cor-baseline-pain-evol).

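### Fisher's exact test in A1.4 ignores the ordering of the pain scores; under stated assumptions it gives up about 20% to 82% of a rank test's power

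*SAP*

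**What the plan says.** SAP 5.1.4 (A1.4) sets out to relate personality and sociodemographic variables to baseline pain: "the pain at baseline (APS, WPS, BPI severity, interference and QLQ-C30) will be assessed". For numeric variables, "Statistical tests for non-zero Spearman's correlation will be used". For the rest, "For categorial variables, exact Fisher tests will be used". It adds "Correction for multiple testing will be applied" without naming a method. The general rule in the SAP introduction is "All hypothesis tests will be conducted at a two-sided alpha level of 0.05, unless otherwise stated".

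The outcomes are all numeric or ordered. Protocol 8.2.4.4 and 8.2.4.5 define APS and WPS on an 11-point scale from 0 to 10. Protocol 8.2.4.1 gives the BPI four severity items and seven interference items, each scored 0 to 10. Protocol 8.2.5 describes the QLQ-C30 as 30 items grouped into scales and single items. Neither A1.4 nor the preprocessing section (SAP 5.1.1, A1.1) says how such a score becomes the columns of a contingency table.

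Two later analyses are related. SAP 5.2.3 (A2.3) and SAP 5.4.2 (I2) use the same wording against the patient's APS slope: "For each feature from the patient characteristics at V1, the correlation will be computed", with a p-value for non-zero correlation and BH correction. The V1 characteristics in SAP 4.2 include sex and study centre. Neither section names a test for nominal features.

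**The concern.** Fisher's exact test is built for two categorical variables. Applied to a 0 to 10 score, it treats 4, 5 and 9 as three unrelated labels; shuffling the columns leaves the p-value unchanged. A difference between men and women in how high they score is the kind of association A1.4 looks for, and the test does not use the information that carries it. The finer the score, the more is lost.

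The plan is also uneven. A numeric trait is tested against pain with a rank method, while a categorical trait is tested against the same pain score with a method that discards rank. Two variables with equally strong associations could then appear very different in the same results table, simply because of the test each was given. In A2.3 and I2 the matter is one of definition: a correlation does not exist for a nominal feature with more than two levels, such as centre.

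**Working it through.** **No figure to reproduce.** The plan states no power for this analysis, and Protocol 4.2.1 says the sample size was not derived from hypothesis tests or precision. The check is therefore a comparison of tests under assumed conditions.

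**Inputs from the documents**
- N = 140, from SAP 2.3: "To confirm the considered sample size of approximately 140 patients completing this study".
- Alpha 0.05, two-sided (SAP introduction).
- APS: integers 0 to 10 (Protocol 8.2.4.4). Entry needs a weekly average of at least 4 (Protocol 5.3, criterion 4), so a 4 to 10 version is also run.
- BPI severity: four items; interference: seven items (Protocol 8.2.4.1).

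**Assumptions not in the documents**
- Two equal groups of 70; 30:70 and four equal groups as variations.
- A normal latent score with a location shift d of 0.4, 0.5 or 0.6 SD (SD 1.6 to 2 points).
- BPI scales scored as item means. Severity then has 10/0.25 + 1 = 41 possible values and interference 10 × 7 + 1 = 71.
- Tabulation either value by value or by a median split.

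**Why granularity matters.** For group sizes n1 and n2 and column totals c_j, the probability of a table is ∏C(c_j, a_j) / C(N, n1), where a_j is the count from group 1 in column j. No term uses the order of the columns. As the c_j shrink towards 1, all tables become equally likely and the p-value moves towards 1.

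**Calibration.** The normal approximation for two means is Φ(d√(n/2) − 1.96) with n = 70. For d = 0.5 this is Φ(2.958 − 1.96) = 0.841; for d = 0.4 and 0.6 it is 0.658 and 0.944. Simulated rank-sum power was 0.61–0.63, 0.81–0.83 and 0.91–0.94, in line with this.

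**Power, N = 140, equal groups, alpha 0.05** (1000 datasets per cell, Monte Carlo error about 1.6 points; cells show d = 0.4 / 0.5 / 0.6)

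| Score | Fisher, raw values | Fisher, median split | Rank-sum |
|---|---|---|---|
| Integers 4–10 | 0.355 / 0.520 / 0.696 | 0.395 / 0.554 / 0.716 | 0.625 / 0.813 / 0.914 |
| Integers 0–10 | 0.263 / 0.441 / 0.627 | 0.387 / 0.588 / 0.726 | 0.626 / 0.820 / 0.923 |
| BPI severity | 0.111 / 0.201 / 0.310 | 0.400 / 0.600 / 0.738 | 0.615 / 0.832 / 0.935 |
| BPI interference | 0.110 / 0.145 / 0.221 | 0.405 / 0.578 / 0.756 | 0.614 / 0.815 / 0.928 |

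**Share of rank-test power lost** = 1 − (Fisher / rank-sum):
- Integers 4–10: 1 − 0.355/0.625 = 43% down to 1 − 0.696/0.914 = 24%.
- Integers 0–10: 1 − 0.263/0.626 = 58% down to 1 − 0.627/0.923 = 32%.
- BPI means: 1 − 0.145/0.815 = 82% down to 1 − 0.310/0.935 = 67%.
- Median split, all scales: 1 − 0.387/0.626 = 38% down to 1 − 0.756/0.928 = 19%.

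**Variations**
- 30:70 split, d = 0.5: Fisher on raw values keeps 0.64 / 0.44 / 0.22 / 0.17 of rank-test power on the four scales in table order, so the largest loss is 83%.
- Alpha 0.01, an assumed stand-in for the unnamed correction (0.05 over five measures): kept share 0.43–0.58 on 4–10, 0.27–0.46 on 0–10, 0.04–0.14 on BPI means, and 0.45–0.64 after a median split.
- Four groups, shifts 0 / 0.25 / 0.5 / 0.75 (400 datasets, error about 2.5 points): Kruskal-Wallis 0.74–0.75, against raw Fisher 0.38 on 4–10 and 0.10 on BPI severity, and 0.53–0.54 after a median split.
- N = 60, equal groups, as sensitivity only because A1 belongs to the final analysis: kept share 0.16–0.50 on raw values, a loss of up to 84%.

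**Type I error.** Null rejection rates were 0.04–0.06 for raw Fisher, 0.02–0.04 after a median split, and 0.025–0.057 for the rank tests. None is inflated.

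**The case against.** The strongest reply is that the size of the loss rests on things the plan does not say. No effect size, split or tabulation rule is given. A statistician could cut the scores before applying Fisher, and the loss is then 19–38%. The legend of Figure 2 in SAP 6.2 covers all pairs of personality and sociodemographic variables, so some Fisher tests may be categorical by categorical, where the method is right. This stands: the loss must be given as a range, and a reader who infers that power is always halved or worse goes too far. It does not remove the defect, because the rank test had more power under both tabulations in every non-null scenario run.

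A reader might also infer that A2.3 and I2 inherit Fisher and, with a continuous slope whose values are all distinct, could never reject. The arithmetic is right for such a test, but neither section mentions Fisher; what they lack is any named test for nominal features. Nor does the plan combine BH with Fisher: BH is named only in A2.3 and I2. Study centre is not clearly within A1.4 either, since SAP 4.2 lists it apart from the sociodemographic variables. Sex is the only clearly categorical A1.4 variable that the documents name.

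Finally, the simulations use location shifts, which favour rank tests. A difference in shape alone could be missed by a rank test and seen by Fisher. That is a fair limit, though A1.4 is framed as a search for correlation with pain level.

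**Conclusion.** The concern holds for A1.4 as a choice of test that wastes information, with a size that depends on assumptions. At N = 140, equal groups, d = 0.4 to 0.6 and alpha 0.05, Fisher gives up about 19% to 82% of rank-test power: 19–38% after a median split, 24–43% on integers 4–10, 32–58% on integers 0–10, and 67–82% on BPI means. QLQ-C30 was not simulated.

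The consequence is limited. A1 is a baseline descriptive analysis serving secondary objectives. It would be tempting to conclude that real associations will be declared absent, or that predictors will be lost to the primary analysis. The SAP supports neither: no rule drops a variable on its A1.4 p-value, and the ridge model in SAP 5.3 (A3) takes the baseline characteristics without an A1.4 filter. In A2.3 and I2 the finding is a missing specification for multi-level nominal features, not a wrong test.

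**What to change.** Replace the Fisher sentence in SAP 5.1.4 with a rule of this kind: for nominal variables against numeric or ordered scores, use the Wilcoxon rank-sum test (two levels) or Kruskal-Wallis (more than two unordered levels); use Spearman for ordinal variables; keep Fisher's exact test for pairs of categorical variables only. Name the same rule for nominal features in SAP 5.2.3 (A2.3) and 5.4.2 (I2). If Fisher on scores is kept for any reason, pre-specify the cut-offs.

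The cost is a few lines in the SAP, with no extra patients or data. The rank methods sit naturally beside the Spearman tests in A1.4 and the Wilcoxon signed rank tests in A2. The one small price is reduced sensitivity to differences in distribution shape without a shift in level.

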1. SYNOPSIS

Title	An Observational Study to Collect Data Characterizing Analgesia in Patients Suffering from Bone Metastasis induced Pain.
Type of Study	Multicentre, observational study.
Study Duration	From screening to end of study, the study duration for each patient will be of a minimum of 5 weeks and a maximum of 12 weeks.
Number of Planned Patients	Up to 180 patients diagnosed with bone metastasis suffering from pain will be enrolled into the study to have up to approximately 140 completers.
Objective	To define predictive factors of pain management/treatments efficacy in cancer patients with bone metastasis suffering from pain (or Cancer-Induced Bone Pain (CIBP)), based on individual patient disease, therapy history and personality traits.
Study Design	The study is an observational, multicentre clinical study that will be conducted in patients with CIBP requiring an analgesic treatment. Up to 180 patients will be enrolled and followed during a period from 4 to 10 weeks of observation. All patients will continue to receive their cancer therapeutic treatments and will be treated for pain relief exactly as they would normally be by the Investigator based on patient needs and clinician practice. During their regular visits to the Investigator, patients will complete questionnaires and Clinical Pain Assessments (CPAs).
Main Diagnosis and Inclusion Criteria	
 • Are men or women of at least 18 years of age. • Patients with bone tumors or bone metastasis from any primary cancer origin that are supported by histological or radiological investigations. • Patients having been or being treated for their bone metastasis and/or their primary cancer. • Patients who require analgesic treatment for unsatisfactory pain relief. • Patients will be required to have a score of at least 4 on the weekly average pain score (WAPS) over the week preceding enrolment.

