The assessments will be performed as described for Visit 1 in the first case scenario up to patient enrolment into the study. After checking WAPS and completion of all inclusion/exclusion criteria, eligible patients will be enrolled in the study and perform the CPAs. The following questionnaires will be completed during this visit: DN4, NPSI, BPI, Expectation and QLQ-C30. The PGAC and IGAC will be completed by the patient and the Investigator, respectively.

At the end of the Visit and after patient evaluation, the Investigator will initiate or review the analgesic treatment and the patients will enter an observational period of 5 to 10 weeks depending on when Visit 1B is scheduled.

Before patients leave the site, Investigator site staff will dispense them a diary and educate them on proper completion of the 2 pain scales, the daily APS and WPS. The APS and WPS of Visit 1A day will be completed by the patients at site with Investigator site staff help. Between Visit 1A and Visit 2, the patients will also be asked to report in their diary intake of supplemental analgesic treatment (rescue analgesic treatment), if any.

Study Visit 1A is depicted in Figure 3.

During this visit, patients will spend about 2 hours at Investigator site.

Abbreviations: BPI = Brief Pain Inventory; DN4= Douleur Neuropathique en 4 questions; ICD= Informed Consent Document; ICD DNA= Informed Consent Document for genotyping research; IGAC=Investigator Global Assessment of Changes; NPSI= Neuropathic Pain Symptom Inventory; PGAC= Patient Global Assessment of Changes; QLQ-C30=quality-of-life questionnaire in 30 questions; WAPS: Weekly Average Pain Score

Figure 3. Sequence of Assessments at Visit 1A

Visit 1B

This visit will start with checking compliance to prescribed analgesic treatment and diary completion instructions. MHLCS, HADS, LOT-R questionnaires and PCS questionnaire will then be completed by the patients. The Investigator will review the analgesic treatment.

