7.2.2.1. Diary

Once a day from enrolment till Visit 2, approximately at the same time of the day in the evening, patients will complete their diary.

The following data will be recorded:

- pain intensity assessment by recording APS and WPS for the last 24 hours (from enrolment till Visit 2 or early discontinuation). See Sections 8.2.4.4 and 8.2.4.5 for further description of APS and WPS,
- any potential event that may help to understand unexpected study outcomes,
- intake of rescue analgesic treatment if any (from enrolment to Visit 2 or early discontinuation).

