8.5.4. COMPLIANCE TO STUDY VISITS

Depending on patient general health status, visits to the Investigator site may occur after enrolment at interval of 2 or 4 weeks. Visits schedule can be adapted according to Investigator-patients agreement, as presented in Tables 1 and 2.

Table 1. Study Visits with Allowed and Suggested Time Intervals – First Case Scenario – Enrolment at Visit 1

Visit Number	Time Interval (Days)	
	Suggested	Allowed
Visit 1 (Screening and Enrolment)	Day 1	
Intermediate Phone Call	Day 15	Day 13 to 17
Optional intermediate evaluation Visit	Day 15	Day 13 to 19
Visit 2	Day 29	Day 29 to 43
Phone Call	Visit 2 Day + 7 days	Visit 2 Day + 14 days

Table 2. Study Visits if with Allowed and Suggested Time Intervals – Second Case Scenario – Enrolment at Visit 1A

Visit Number	Time Interval (Days)	
	Suggested	Allowed
Visit 1A (Screening and Enrolment)	Day 1	
Visit 1B	Day 8	Day 8 to 29
Intermediate Phone Call	Visit 1B Day + 14 days	Visit 1B Day + 12 to 16 days
Optional intermediate evaluation Visit	Visit 1B Day + 14 days	Visit 1B Day + 12 to 18 days
Visit 2	Visit 1B Day + 28 days	Visit 1B day + 28 to 42 days
Phone Call	Visit 2 Day + 7 days	Visit 2 Day + 14 days

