1.1 Responsibilities

1.2Changes from Protocol

- A secondary endpoint was added for the analgesic treatment efficacy: Patient's daily APS and the linear regression coefficient of its daily evolution
- Secondary objectives of the final study were precised, while they were absent from the protocol

1.3Amendment Rationale

The primary study objective is the prediction of individual analgesic treatment efficacy. All primary and secondary endpoints concerning treatment efficacy were based on differences between weekly average of pain measures at baseline and at the end of the follow-up period. Due to frequent changes in the analysis therapy of cancer patients with bone metastases, it is essential to have a temporal granularity finer than the 4 weeks (i.e. follow-up duration). Therefore an additional endpoint was added for describing the daily values of APS and its linear trend throughout follow-up.

No secondary objective was described in the study protocol. For the sake of clarity, the current analysis plan describes 3 secondary objectives, all of which can be considered as intermediary milestones necessary in order to reach the (unmodified) primary objective of the study.

2 Study objectives

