The linear approximation of APS was chosen in order to describe the globally increasing or decreasing trend, while keeping easily interpretable results and avoiding overfitting. How to measure these values for one patient p:

- consider a model $APS_p(t) = a_{p0} + a_{p1} t$ where p is one patient and t is the time (in days since inclusion of patient p)
- Fit weights a_{pi} by linear regression on the patient's data (one dataset per patient, one record per timepoint)
- The variability around trend is measured by the per-patient RMSE of the linear model

Univariate statistics (mean, standard deviation (SD), median, first and third quartiles) on the distribution of these variables will be reported in Table (tab-pain-evol-distr). A one-sample Wilcoxon signed rank test will be performed in order to determine whether the linear trend in APS is globally different from zero. In addition, visualisation of the patients based on these 3 features will be performed in Figure (5).

A2.2: Summary of individual analgesic treatment evolution 5.2.2

Based on the description of analysic therapy in the patient diary, the daily number of distinct drugs will be computed as well as the daily number of distinct drug categories. Treatment doses will be ignored for this analysis. The same feature extraction as in A2.1 will be performed on these daily numbers of drugs in order to obtain a per-patient average and linear trend of the number of drugs.

Univariate statistics (mean, standard deviation (SD), median, first and third quartiles) on the distribution of these variables will be reported in Table (tab-treat-evol-distr). A one-sample Wilcoxon signed rank test will be performed in order to determine whether the linear trend in number of analgesics is globally different from zero. In addition, visualisation of the patients based on these features will be performed in Figure (6).

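### The per-patient APS slope in A2.1 is fitted over follow-up that may run from 28 to 70 days, so slopes are not comparable across visit schedules

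*SAP*

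**What the plan says.** SAP section 5.2.1 (A2.1) reduces each patient's APS curve to a mean, a linear trend and the scatter around that trend. In the model, "t is the time (in days since inclusion of patient p"), and the instruction is "Fit weights a_{pi} by linear regression on the patient's data", each patient being fitted separately. No window, truncation, weighting or adjustment for follow-up length is given. A2.2 applies the same extraction to daily drug counts.

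The daily APS comes from the diary, completed "Once a day from enrolment till Visit 2" (Protocol 7.2.2.1). Protocol 8.5.4 allows Visit 2 on Day 29 to 43 when all Visit 1 assessments are done at one visit. When they are split, Visit 1B falls on Day 8 to 29 and Visit 2 at "Visit 1B day + 28 to 42 days". The Synopsis has patients "followed during a period from 4 to 10 weeks of observation", and Protocol 4.1.1 says of the split schedule that "the patients will enter an observational period of 5 to 10 weeks depending on when Visit 1B is scheduled".

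The SAP's amendment rationale (section 1.3), which introduces the slope endpoint, says "it is essential to have a temporal granularity finer than the 4 weeks (i.e. follow-up duration").

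The slope is a secondary endpoint (SAP 2.5). A2.1 tests it against zero with a Wilcoxon signed rank test. A2.3 and interim analysis I2 correlate it with every patient characteristic at V1, with Benjamini-Hochberg (BH) correction. Study centre is on that list (SAP 4.2).

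**The concern.** A straight line summarises a curve faithfully only over a stated interval. If the curve bends, the fitted slope depends on where the interval ends, and here each patient's visit schedule sets that end. The SAP itself calls the line an approximation. Analgesic treatment is started or reviewed at enrolment in patients with a weekly average pain score of at least 4, so an early fall followed by flattening is plausible, though neither document predicts it.

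The schedule is not random. Protocol 4.1 lets it depend on patient and site availability. A V1 feature that differs between schedules could then correlate with the slope without any link to pain response, and centre is the obvious candidate. The slopes also differ in precision, yet they enter the test and the correlations with equal weight.

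**Working it through.** **1. Follow-up windows (Protocol 8.5.4, Tables 1 and 2), in days after Day 1**

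- One-visit schedule: 29 − 1 = 28 to 43 − 1 = 42; suggested 28.
- Split schedule: (8 + 28) − 1 = 35 to (29 + 42) − 1 = 70; suggested 35.

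These reproduce the protocol's 4 to 10 weeks and 5 to 10 weeks. Adding the closing phone call gives 28 + 7 = 35 days and 70 + 14 = 84 days, the Synopsis total of 5 to 12 weeks. The range of 28 to 70 days is therefore what the protocol intends.

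**2. Effect of the window on the slope**

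For daily records t = 0, …, T, slope(T) = Σ(t − T/2)·APS(t) / Σ(t − T/2)². The documents give no pain course. Assume APS(t) = 6 − 2(1 − exp(−t/τ)); the size of the fall cancels in the ratios.

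| τ (days) | slope, 28 d | 35 d | 42 d | 70 d | 28 v 35 | 28 v 42 | 28 v 70 |
|---|---|---|---|---|---|---|---|
| 7 | −0.0579 | −0.0431 | −0.0330 | −0.0144 | 1.35 | 1.76 | 4.04 |
| 10 | −0.0605 | −0.0474 | −0.0378 | −0.0180 | 1.28 | 1.60 | 3.36 |
| 14 | −0.0584 | −0.0481 | −0.0400 | −0.0212 | 1.21 | 1.46 | 2.75 |

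A linear course gives 1.00 in every comparison. For 28 v 70 days, slower decay (τ = 21 or 28) gives 2.16 or 1.86, and very fast decay (τ = 2) gives 5.47. A late rebound can reverse the sign.

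**3. Precision, whatever the shape**

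With independent daily errors of equal variance, the slope variance is proportional to 1/Σ(t − T/2)², and that sum equals n(n² − 1)/12 with n = T + 1.

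- 28 days: 29 × 840/12 = 2,030
- 35 days: 36 × 1,295/12 = 3,885
- 70 days: 71 × 5,040/12 = 29,820

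The 28-day slope has 29,820/2,030 = 14.7 times the variance of the 70-day slope, and 3,885/2,030 = 1.9 times that of the 35-day slope.

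**4. Spurious correlation**

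Simulation with n = 140, half of patients per schedule, τ = 10, fall with mean 2 and SD 1.5 points, daily error SD 1.2, and no link between feature and fall. A2.3 names no correlation coefficient; Spearman was used, as in A1.4. Only n comes from the documents. Unadjusted rejection rates at the 5% level:

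| Setting | Rate |
|---|---|
| Visits spread over the allowed windows, feature differs by 0.5 SD between schedules | 11 to 14% |
| Same, 0.8 SD | 19 to 21% |
| Suggested visit days, 0.5 SD | 6 to 7% |
| Common window of 28 days, 0.5 SD | about 5% |

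Changing one input of the first row at a time gives about 7 to 8% with 20% of patients on the split schedule, 6 to 7% with a 0.2 SD feature difference, and 6 to 7% with a mean fall of 1 point.

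**The case against.** A reader might infer that visit schedule alone changes the slope three- to four-fold as a general fact. The documents do not support that. It needs a fall-then-plateau course and a comparison of the shortest allowed window with the longest. Seventy days arises only when Visit 1B and Visit 2 are both as late as permitted. The documents point to a less tidy course: Protocol 3.2 describes ongoing bone pain as growing with time, and the SAP stresses frequent changes of therapy. This objection stands and limits the size of the problem.

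The false-positive rates rest on inputs the documents do not give, and they shrink quickly under milder ones. They are also per-test rates, whereas A2.3 and I2 apply BH correction. The first part stands. The second does not remove the problem, because BH presupposes p-values that are valid under the null and confounding by schedule makes them invalid.

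The reach is limited. The primary endpoint is a change in weekly means, and A3 models the APS difference between days with and without a treatment; neither uses the slope. For a monotone course the sign of the slope does not depend on the window, so the null hypothesis of the Wilcoxon test is largely unaffected.

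Finally, the endpoint was added to describe the trend throughout follow-up, and a 28-day window narrows that target. This is a real cost, which a full-follow-up sensitivity analysis meets in part.

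**Conclusion.** The concern holds as a matter of comparability. The plan leaves the fitting window to each patient's schedule, the protocol lets it run from 28 to 70 days, and the SAP was written as though it were 4 weeks.

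The unequal precision needs only the assumption of independent daily errors. The slope distortion also needs curvature. For an assumed plateau course with a time constant of 7 to 14 days it is several-fold only at the extremes, about 1.5 to 1.8 within the one-visit schedule (28 v 42 days), modest at the suggested days, and absent for a linear course. The inflation of false positives in A2.3 and I2 further depends on how many patients use each schedule and how much their features differ, which the documents do not say.

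This should be corrected, but it affects a secondary endpoint and the correlation screens built on it. Nothing here supports the inference that the primary endpoint or the predictive models are compromised.

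**What to change.** - In SAP A2.1 and A2.2, compute the mean, linear trend and RMSE on Day 1 to Day 29 for every patient, and use these in A2.3 and I2. Every completer seen within the allowed windows reaches Day 29, so none is lost, and the same course then gives the same slope under every schedule.
- Repeat on full follow-up as a sensitivity analysis, with follow-up length as a covariate. This keeps the trend throughout follow-up that the endpoint was added to describe.
- Say whether the APS given at the closing phone call, 7 to 14 days after Visit 2, enters the full-follow-up fit. If it does, the longest window becomes 70 + 14 = 84 days.
- Correct the 4-week follow-up statement in SAP 1.3 to agree with the protocol.

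The cost is a few sentences in the SAP and one repeated analysis. The downside is that diary days after Day 29, including those after a treatment review at a late Visit 1B, count only in the sensitivity analysis.
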